2.3.4 Rounding of derived variables

Derived variables will be rounded to the appropriate number of decimals at display level:

- Cumulative prednisone dose will be rounded to 0 decimals.
- BMI and time since diagnosis will be rounded to 1 decimal.
- eGFR and NCPD will be rounded to 2 decimals.

2.3.5 Outliers

There will be no outlier detection. All measured values will be included in the analyses.

	Statistical Analysis Plan	
ARGX-113-1904	Final analysis	Final 2.0 of 22NOV2023

2.4 PRESENTATION OF RESULTS

Region/country specific outputs will be created to support region/country specific submissions.

Specifically, all descriptive outputs described in this SAP will be repeated by region (Japanese / Non-Japanese as defined in the study protocol) to support the J-MAA submission. The definition of a Japanese participant in the protocol is a participant whose parents and 4 grandparents are Japanese, who has the Japanese nationality, was born in Japan, has not lived outside of Japan for a total of >10 years, and currently lives in Japan.

To support the Chinese submission, all outputs described in this SAP will be repeated for the following two subpopulations: Mainland Chinese and East Asian. Mainland Chinese is defined as any participant enrolled by an investigational site located in mainland China and with a race “Asian”. East Asian is defined as any participant enrolled by an investigational site located in East Asia (China, Japan), and with a race “Asian”. In addition, the Pharmacokinetics and Pharmacodynamics analyses described in sections 4.2 and 4.3 (except the Japanese-specific analysis) will be repeated for the complement of the Mainland Chinese and East Asian subgroups (i.e. Non-Mainland Chinese and Non-East Asian).

To support the EU submission, all outputs described in this SAP will be repeated for the participants with a history of relapsing disease. This subgroup includes participants that met the following inclusion criteria in the protocol of study ARGX-113-1904:

- 4 iii. Experiencing flare with PDAI activity score ≥ 15 , a maximum of 4 years since disease onset, and off prednisone therapy \pm a conventional immunosuppressant (eg, azathioprine, cyclophosphamide, methotrexate, mycophenolate mofetil) or dapsone.
- 4 iiiii. Experiencing flare with PDAI activity score ≥ 15 , a maximum of 4 years since disease onset, and receiving a tapered dose of oral prednisone (or equivalent), provided that prednisone has been given at stable dose \pm a conventional immunosuppressant (eg, azathioprine, cyclophosphamide, methotrexate, mycophenolate mofetil) or dapsone for at least 2 weeks and participants are fit to start prednisone treatment at 0.5 mg/kg qd at baseline.

2.4.1 *Calculation of descriptive statistics and percentages*

For continuous variables, full descriptive statistics will only be presented if there are at least 2 non-missing observations. Alternatively, only the number of non-missing data points and mean are shown.

Descriptive statistics will include the number of non-missing data points, the arithmetic mean, the standard deviation (SD), the standard error (SE), the median, minimum, Q1, Q3 and maximum.

Descriptive statistics for immunogenicity titer values will also include geometric mean (GM) and geometric standard deviation (GSD).

	
Statistical Analysis Plan
	

ARGX-113-1904
	
Final analysis
	
Final 2.0 of 22NOV2023

Mean, median, Q1 and Q3, geometric mean (GM) and geometric standard deviation (GSD) will be presented with one more decimal place than the individual values, with maximum 4 decimal places. SD and SE will be presented with 2 more decimal places than the individual values, with maximum 5 decimal places. Minimum and maximum will be presented with the same number of decimal places than the individual values, with maximum 3 decimal places. GM and GSD of percent changes from baseline are presented with one decimal.

Descriptive statistics for PK concentrations will include n (number of observed values), arithmetic mean, SD, median, minimum and maximum, and the coefficient of variation (CV%). Serum concentrations will be presented with 3 significant digits in the original concentration units, except values ≥ 1000 , which will be presented without the decimals. The descriptive statistics should be rounded to the same number of significant digits as the individual values. If more than half of the values are BLQ, arithmetic mean will be set to BLQ and SD and CV% will not be calculated.

For event-type safety data, the number and percentage of participants with an event, and the number of events will be shown. The denominator will be all participants in the analysis set per treatment and phase (and period in case of AE's).

For frequency tabulations and cross-tabulations, the denominator will be all participants in the analysis set per treatment. For tables where results are shown by analysis visit, the denominator will be all participants in the analysis set per treatment and per analysis visit. Missing values will never be included in the denominator count when computing percentages. For cross-tabulations of post-baseline results versus baseline results, a 'missing' category will be shown for baseline results if applicable.

2.4.2 Presentation of treatments

The following treatment labels will be used in the tables and listings:

- EFG PH20 SC
- PBO PH20 SC

In the general characteristics analysis, a grand total will be added to summarize all participants over treatments. Grand totals will be shown last.

2.4.3 Order in tables and listings

All tables and figures will be presented per treatment, unless specified otherwise. In by visit displays, worst-case will be shown last, if present.

In listings for general characteristics, results will be ordered by treatment and participant, unless specified otherwise.

All other listings will be ordered by treatment, participant, analysis visit and time point, unless specified otherwise.

In tables showing several parameters, each parameter will begin on a new page and parameters will be sorted alphabetically, within the parameter category if applicable.

The Efgartigimod treatment group will always be shown first, then the Placebo treatment group.

	Statistical Analysis Plan	
ARGX-113-1904	Final analysis	Final 2.0 of 22NOV2023

3. GENERAL CHARACTERISTICS ANALYSES

3.1 PARTICIPANT DISPOSITION

3.1.1 *Available data*

The following participant data will be tabulated:

- The number of participants in each analysis set.
- The number and percentage of participants for each phase and analysis visit.
- Descriptive statistics of the phase duration, calculated as phase end date – phase start date + 1 day. Duration of ‘on treatment’ phase will also be presented for participants with/without treatment failure.
- The number and percentage of participants who completed or discontinued the study as documented on the study termination page and the number and percentage of participants for each study discontinuation reason.
- The number and percentage of participants who completed or discontinued the treatment as documented on the end of treatment page and the number and percentage of participants for each treatment discontinuation reason.
- The number and percentage of participants who roll over to study ARGX-113-1905 and the number and percentage of participants by reason not rolling over (i.e. ‘not eligible’, ‘not willing to’ and ‘other’).

All information collected in the CRF concerning treatment allocation and study and treatment discontinuation will be listed.

3.1.2 *Presentation of results*

Tables to be produced for the topline results (see list of output in 8.1) will be presented for all participants (PV+PF) as well as for PV participants and PF participants separately.

3.2 DEMOGRAPHIC AND OTHER BASELINE CHARACTERISTICS

3.2.1 *Available data*

The following parameters will be available:

- Demographics: sex at birth, age at informed consent, race and ethnicity (if collection permitted), region, childbearing potential, height, weight and BMI at screening, year of birth, date of signing ICF (listed only).

	
Statistical Analysis Plan
	

ARGX-113-1904
	
Final analysis
	
Final 2.0 of 22NOV2023

- Baseline disease characteristics: date of pemphigus onset (listed only), date of pemphigus diagnosis, pemphigus type (vulgaris/foliaceus) and subtype (mucosal-dominant / mucocutaneous / cutaneous), type of procedure used for confirmation of diagnosis (cutaneous histology / direct immunofluorescence / indirect immunofluorescence / ELISA), relapsing (yes / no), newly diagnosed (yes / no), number of relapses (if applicable), prior use of immunosuppressants (yes / no), prior use of rituximab (yes / no), PDAI activity score and PDAI total score at baseline, baseline severity [PDAI activity <30/≥30 as well as PDAI activity score 15-44 (moderate), ≥45 (severe)], ABQOL total score at baseline, Karnofsky performance score, positive (≥ 20 RU/ml) anti-Dsg antibodies (aDsg1 only, aDsg3 only, both aDsg1 and aDsg3, neither aDsg1 nor aDsg3), prednisone equivalent dose per body weight at baseline (mg/kg/day), prednisone equivalent dose at baseline (mg/day) and stratification factors (as randomized).

3.2.2 Derivation rules

The following parameters will be derived:

- Time since pemphigus diagnosis (months): (date of first IMP – date of diagnosis)*12/365.25

Notes:

- Partially missing dates will be imputed as detailed in section 2.3.2.
- Result will be rounded as detailed in section 2.3.4 .
- Prior use of immunosuppressants is defined as use of medications with ATC level 2 = ‘IMMUNOSUPPRESSANTS’ and start date prior to first IMP administration
- Prior use of rituximab is defined as use of medication with CMDECOD = ‘RITUXIMAB’ and start date prior to first IMP administration
- Derivation of prednisone equivalent dose is detailed in section 3.5.2. Since day 1 can be considered as a transition day, prednisone equivalent dose on day 2 will be used as baseline.
- Region: North America (USA), Europe (Bulgaria, France, Hungary, Germany, Greece, Italy, Poland, Romania, Spain, UK), Asia (China, India, Japan), Rest of world (Australia, Georgia, Russian Federation, Serbia, Turkey, Ukraine)

3.2.3 Presentation of results

Demographics will be presented using descriptive statistics for age, height, weight and BMI at screening and frequency tabulations for sex, childbearing potential, weight at baseline (<77.5 kg, ≥77.5 kg), geographical region, race and ethnicity.

Baseline disease characteristics will be presented using descriptive statistics for time since diagnosis (overall and for newly diagnosed subjects and subjects relapsing), number of relapses, PDAI activity score and PDAI total score at baseline, ABQOL

	
Statistical Analysis Plan
	

ARGX-113-1904
	
Final analysis
	
Final 2.0 of 22NOV2023

total score at baseline, Karnofsky performance score and prednisone dose; frequency tabulations for all other parameters.

Descriptive analyses will be presented for all participants (PV+PF) as well as for PV participants and PF participants separately.

All demographic data and baseline disease characteristics will be listed.

3.3 MEDICAL HISTORY AND CONCOMITANT DISEASES

3.3.1 Available data

Medical history findings are coded using the medical dictionary for regulatory activities (MedDRA) into system organ classes and preferred terms. For each finding, a start and stop date or ongoing flag is collected. The MedDRA version will be updated to the latest one until the database lock of 1904.

3.3.2 Derivation rules

Medical history finding: not ongoing at screening, ended before date of signing informed consent.

Concomitant disease: medical history condition still ongoing at screening.

3.3.3 Presentation of results

Medical history and concomitant diseases will be tabulated separately. Both tables will show:

- The number and percentage of participants with findings
- The number and percentage of participants with findings by system organ class (SOC) and preferred term (PT)

All medical history (not ongoing at screening) and concomitant disease (still ongoing at screening) data will be listed.

3.4 PRIOR AND CONCOMITANT THERAPIES AND PROCEDURES

3.4.1 Available data

All therapies are coded using WHO-DD. Anatomical-Therapeutic-Chemical (ATC) selection is performed to select the most appropriate medication class. For the selected class, ATC coding up to level 4 is available in the clinical database. For each therapy, a start date or prior flag and stop date or ongoing flag are collected.

Procedures are coded using the medical dictionary for regulatory activities (MedDRA) into preferred terms. For each finding, the indication and a start and stop date are collected.

3.4.2 Derivation rules

Based on their start and stop date, therapies and procedures will be allocated into one or both of the following categories:

	
Statistical Analysis Plan
	

ARGX-113-1904
	
Final analysis
	
Final 2.0 of 22NOV2023

- Prior: any therapy/procedure that strictly started before the first dose.
- Concomitant: any therapy/procedure that was taken on or after the first dose.

A medication that started before the first dose date and continued during the study will be classified as both prior and concomitant.

Therapies/procedures with (partially) missing date(time)s will be allocated to each category unless the available parts of the therapy/procedure start or stop date(time) provide evidence not to do so.

Intercurrent events of unallowed therapies that may influence efficacy are defined as:

- Immunosuppressants at therapeutic doses for at least 4 weeks in total
- IVIg/SCIg at immunomodulating dose (≥ 1 g/kg/month)
- Immunoabsorption or plasma exchange, at least 1 procedure
- Rituximab or other anti-CD20 biologics, at least 1 infusion
- IV or IM corticosteroids
- Tetracyclines at least 100 mg/day for at least 2 weeks in total
- Any interventional study drug under development for pemphigus

Note: if dose is missing and/or period of intake cannot be derived, it is still considered an intercurrent event.

Details on the derivation of intercurrent events are provided in Appendix 9.1. More information how these intercurrent events are handled can be found in the efficacy section 4.1.

3.4.3 *Presentation of results*

Prior and concomitant therapies will be tabulated (separately), by ATC class (level 1 and 3) and generic term. Concomitant therapies will exclude oral Prednisone and equivalent medications administered for pemphigus; these will be presented separately.

Tables to be produced for the topline results (see list of output in 8.1) will be presented for all participants (PV+PF) as well as for PV participants.

All prior and concomitant therapies/procedures data will be listed with detailed information about ATC classes.

3.5 IMP AND PREDNISONE ADMINISTRATION

3.5.1 *Available data*

For each IMP administration and for prednisone administration, the start and end date/times, doses (per administration), dose units and volume with units (for IMP only) will be recorded.

Participants/caregivers may follow a self-administration training. Visits at which training took place and reasons for not following a training are recorded.

	Statistical Analysis Plan	
ARGX-113-1904	Final analysis	Final 2.0 of 22NOV2023

3.5.2 Derivation rules

The following parameters will be derived for IMP administration:

- Number of administrations: sum of all administrations of study drug. [REDACTED] administrations are expected on day 1 and day 8.
- Number of [REDACTED] doses: i.e. daily doses of [REDACTED] mg [REDACTED] administrations of 1000 mg).

The following parameters will be derived for IMP self-administration by participant and by caregiver:

- Number of participants/caregivers receiving the self-administration training.
- Number of training visits received by participant/caregiver.
- Number of participants/caregivers who were adequately trained and capable to self-administer efgartigimod.
- Number of training visits before being considered capable to self-administer.

Normalised cumulative Prednisone dose (NCPD) will be calculated based on prednisone equivalent doses (Schimmer e.a., 2015, and Liu e.a., 2013). Prednisone equivalent dose is calculated as [dose of ATC]*[equivalence factor prednisone]/[equivalence factor ATC]. Following [equivalence factors] are used:

	
Statistical Analysis Plan
	

ARGX-113-1904
	
Final analysis
	
Final 2.0 of 22NOV2023

- Betamethasone [1.5]
- Cortisone [37.5]
- Deflazacort [15]
- Dexamethasone [1.5]
- Fluocortolone [10]
- Hydrocortisone [30]
- Methylprednisolone [8]
- Methylprednisolone acetate [8]
- Methylprednisolone sodium succinate [8]
- Paramethasone [4]
- Prednisolone [10]
- Prednisolone acetate [10]
- Prednisolone sodium succinate [10]
- Prednisone [10]
- Prednisone acetate [10]
- Prednylidene [12]
- Rimexolone [20]
- Triamcinolone [8]

Example: calculation of equivalent dosage of 12 mg methylprednisolone: $12 * 10 / 8 = 15$ mg prednisone.

Only systemic use of oral medication is included.

NCPD (mg/kg/day) is calculated for different periods as [the sum of (equivalent doses taking into account daily dose frequency)/(body weight in kg)]/(period duration in days) with body weight of visit closest before or at each start of prednisone equivalent medication record. If for a given day of analysis period, no record exists in the CRF indicating prednisone use that day, the dose will be assumed to be 0 mg. NCPD will be calculated with and without considering main intercurrent events (see efficacy section 4.1.2.2). Additionally the cumulative prednisone dose (in mg) over these periods will be calculated. Following periods are considered (including start and end of the period):

- Whole planned treatment phase, defined as the period from Day 1 to Day 218 (regardless of whether the assessment is on treatment or follow up phase)
- Start of treatment phase until CR in participants who achieved CR (up to Day 218)
- Start of treatment phase until CRmin in participants who achieved CRmin (up to Day 218)

Days with prednisone equivalent dose ≤ 10 mg and ≤ 20 mg will be flagged in the analysis dataset. The number of days with prednisone equivalent dose ≤ 10 mg in

	Statistical Analysis Plan	
ARGX-113-1904	Final analysis	Final 2.0 of 22NOV2023

the treatment phase will be calculated as well as the proportion of days ≤ 10 mg in the treatment phase ($=100 * \text{number of days } \leq 10 \text{ mg} / \text{duration of treatment phase}$).

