6.6. Continued Access to Study Intervention After the End of the Trial

Efgartigimod PH20 SC or placebo SC will be administered subcutaneously until CRmin. Participants at the EoS visit or ED visit in trial ARGX-113-1904 will be given the option to enroll into the OLE trial ARGX-113-1905 after confirmation of eligibility, while retaining the blinding of trial ARGX-113-1904. For each participant, the date of the baseline visit in the OLE trial ARGX-113-1905 will be the same as the date of the EoS visit in trial ARGX-113-1904. There is no need to schedule an additional visit for a roll over visit. At baseline of the OLE study, participants will be treated according to their clinical status at entry of the OLE trial ARGX-113-1905, as defined in the trial protocol.

Week 34 (follow-up visit 1) or week 38 (follow-up visit 2) is the EoS for participants who do not enroll in the OLE trial ARGX-113-1905. The week 38 follow-up visit will only be required for those participants who were still receiving IMP at least 1 visit between week 26 and EoS/ED. For participants who ended treatment prior to week 26, week 34 will be the EoS visit.

If a participant withdraws/discontinues early and does not roll over to the OLE trial (ARGX-113-1905), usual treatment will be administered, if required, in accordance with the trial site's standard of care and generally accepted medical practice depending on the participant's individual needs. Depending on the clinical status of the participant and the clinical judgment from the investigator, completion of the treatment-free follow-up period may be performed.

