Participants who experience treatment failure, or flare after achieving CRmin, will be allowed to roll over into the OLE study ARGX-113-1905 earlier than week 30. Participants who do not roll over into study ARGX-113-1905 will complete an 8-week treatment-free follow-up period. Participants experiencing an SAE related to prednisone in ARGX-113-1904 are considered treatment failures and may also benefit from an early roll over to the OLE, according to clinical judgment of the investigators.

	Statistical Analysis Plan	
ARGX-113-1904	Final analysis	Final 2.0 of 22NOV2023

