4.1.2.2 KEY SECONDARY ENDPOINTS (ALPHA CONTROLLED)

The following key secondary endpoints, which will be tested in the mITT population in hierarchical order (see section 4.1.4), are defined as:

- 1) The proportion of PV+PF participants that have achieved CRmin within 30 weeks using the same stratified CMH as for the primary endpoint. As this first key secondary endpoint is similar to the primary endpoint, the same approach for handling the main ICEs (both composite strategy and treatment policy strategy), as suggested for the primary analysis, will be applied.
- 2) Normalised cumulative Prednisone dose (NCPD, mg/kg/day) over the whole planned treatment phase in PV participants, will be analyzed by an analysis of covariance (ANCOVA) model to compare both treatment groups. Only actual administrations of prednisone are considered (not as scheduled). The model will include treatment and the stratification variables will be considered as factors.

Main intercurrent events are handled using the hypothetical strategy, that is, as follows:

- Intercurrent medications (see section 3.4.2): stop calculating cumulative dose after ICE. In case 'immunosuppressants for at least 4 weeks in total' is the ICE, use end of the 4 weeks IC medication as stop for cumulative dose calculation. In case ‘tetracyclines for at least 2 weeks in total' is the ICE, use end of the 2 weeks IC medication as stop for cumulative dose calculation. In case ‘IV or IM corticosteroids ' is the ICE, use the first day of this IC medication as stop for cumulative dose calculation.
- Discontinuation of IMP before CRmin due to lack of efficacy: stop calculating cumulative dose after this ICE.

Details on the derivation of intercurrent events are provided in Appendix 9.1.

	Statistical Analysis Plan	
ARGX-113-1904	Final analysis	Final 2.0 of 22NOV2023

A non-parametric stratified Mann-Whitney test will be performed as sensitivity analysis.

A supplementary analysis for this secondary endpoint will use the ‘treatment policy strategy’ where the occurrence of the intercurrent event is considered irrelevant: NCPD is calculated regardless of whether or not the intercurrent event occurs.

3) Time to CR in PV participants, calculated as the difference between the first date CR was achieved and the first IMP administration date.

Time to CR (days) = date (first CR) - first IMP date + 1

Main intercurrent events are handled as follows (composite strategy):

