9. APPENDICES

9.1 MAIN INTERCURRENT EVENTS (ICE)

The conditions below are tailored for the primary endpoint (CRmin). Conditions based on medication type, minimal dosing and minimal duration apply to the other endpoints with composite strategy or hypothetical strategy. However, conditions like “in the last 12 weeks before achieving CRmin” are specific for CRmin only. For these strategies, NCPD is calculated until and excluding the first day of ICE unless specified otherwise.

9.1.1 *Immunosuppressants or dapsone at therapeutic doses for at least 4 weeks in total in the last 12 weeks before achieving CRmin*

- Azathioprine, at least 1 mg/kg/day
- Mycophenolate mofetil, at least 2 g/day
- Mycophenolic acid, at least 1000 mg/day
- Mycophenolate mofetil hydrochloride, at least 2 g/day
- Cyclophosphamide, at least 1 mg/kg/day, or IV pulse 500 mg/month
- Methotrexate (sodium), at least 5 mg/week (in Japan), whereas 10 mg/week in Europe
- Ciclosporin, at least 3 mg/kg/day
- Dapsone, at least 1 mg/kg/day
- Hydroxychloroquine sulfate, at least 400mg/day
- Thalidomide, at least 50mg/day

For CRmin and time to CRmin these events should occur in the last 12 weeks before CRmin to be considered as an ICE. NCPD is calculated until and including the last day of the applicable 4 weeks intake.

9.1.2 *IVIg/SCIg at immunomodulating dose (≥ 1 g/kg/month) before achieving CRmin*

- ‘Immunoglobulins NOS’ or ‘Immunoglobulin G Human’ or ‘Immunoglobulins’ or ‘Immunoglobulin Human Normal’ or ‘Anti-D Immunoglobulin
and cmroute=’INTRA VENOUS’ or ‘SUBCUTANEOUS’.

9.1.3 *Immunoabsorption or plasma exchange (at least 1 procedure) before achieving CRmin*

- ‘Plasmapheresis’ or ‘Immunoabsorption therapy’ as PRDECOD, at least one cycle

	Statistical Analysis Plan	
ARGX-113-1904	Final analysis	Final 2.0 of 22NOV2023

9.1.4 *Rituximab or other anti-CD20 biologics (at least 1 infusion) before achieving CRmin*

- Rituximab, at least one cycle of 1 g or 375 mg/m²
- Obinutuzumab
- Ofatumumab
- Ocrelizumab
- Ibritumomab tiuxetan
- Veltuzumab
- Tocilizumab

9.1.5 *IV or IM corticosteroids*

- administered (at least 1 administration, any dose) once the participant has achieved minimal prednisone (or prednisone equivalent) dose of ≤ 10 mg/day (i.e., during the 8 week period required in the protocol to confirm the CRmin status) or administered at any moment before achieving CRmin in any of the three following situations:
 - a) more than 60 mg of prednisone equivalent for 3 consecutive days

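### NCPD is averaged over a fixed Day 1 to 218 and, read literally, scores days after a participant has left the trial as 0 mg prednisone

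*SAP*

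**What the plan says.** The tested period in SAP 3.5.2 is the "Whole planned treatment phase, defined as the period from Day 1 to Day 218", whether a dose falls in the treatment or the follow-up phase. The sum of daily doses per kg is divided by the period duration. If on a given day "no record exists in the CRF indicating prednisone use that day, the dose will be assumed to be 0 mg".

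For intercurrent events (ICEs), SAP 4.1.2.2 lists intercurrent medications and one discontinuation rule: "Discontinuation of IMP before CRmin due to lack of efficacy: stop calculating cumulative dose after this ICE". Appendix 9.1 adds that "NCPD is calculated until and excluding the first day of ICE unless specified otherwise". The supplementary treatment-policy analysis ignores ICEs.

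Early exit is part of the design. Protocol 4.1 allows rollover to 1905 before W31 for treatment failure, a flare after CRmin or a prednisone-related SAE. Protocol 6.6 states that "the date of the baseline visit in the OLE trial ARGX-113-1905 will be the same as the date of the EoS visit". In SAP 2.2.1 (Table 1), rollover participants have no 1904 follow-up phase. No section brings 1905 doses into NCPD.

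For therapies in general, SAP 3.4.1 says that "a start date or prior flag and stop date or ongoing flag are collected".

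Protocol 9.5.7 normalises by days in study, and its formula divides by days treated.

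**The concern.** A day with no prednisone record can mean two things: the participant was observed and took none, or was no longer in 1904. The rule treats both as 0 mg and keeps the divisor at 218. Leaving early therefore lowers the score whatever dose is taken afterwards.

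In the tested analysis the rule applies to exits outside the NCPD list of ICEs: early rollover for a flare after CRmin, rollover for a prednisone-related SAE not coded as lack of efficacy, and withdrawal for other reasons. In the treatment-policy analysis it applies to every early exit.

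NCPD in PV is third in the fixed sequence of SAP 4.1.4 and gates five later tests. NCPD in PV+PF is sixth. What is at stake is the meaning of an alpha-controlled estimate of steroid sparing.

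**Working it through.** The documents give no expected value, standard deviation or power for NCPD, so there is no planned figure to reproduce. The check applies the SAP formula to dose paths built from protocol Table 3. The paths are illustrative and used for arithmetic only.

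**Formula.** NCPD = sum of daily mg / (weight × 218). At 75 kg the denominator is 75 × 218 = 16,350.

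**Flare after CRmin (not an NCPD ICE).** Assume 75 kg and CR on Day 42. Doses are 35 mg for 56 days, 20 mg for 14 days, then 17.5, 15 and 12.5 mg for 7 days each, and 10 mg from Day 92. CRmin falls on Day 147. Up to Day 91 the sum is 1,960 + 280 + 315 = 2,555 mg.

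| Path | 10 mg held | Protocol 4.2 recommended taper after CRmin |
|---|---|---|
| Flare, rollover Day 165 | 2,555 + 74×10 = 3,295 mg → **0.202** | 2,555 + 560 + 18×7.5 = 3,250 mg → **0.199** |
| Remission to Day 211 (W31) | 2,555 + 120×10 = 3,755 mg → **0.230** | 2,555 + 560 + 28×7.5 + 28×5 + 8×2.5 = 3,485 mg → **0.213** |

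The two paths are identical to Day 165, so the gap is simply the dose that is no longer recorded: 460 mg held, 235 mg with taper. A dose increase recorded in 1904 before rollover would have to add more than that to reverse the order.

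**Other weights.** The 50–75 kg columns also reach CRmin on Day 147, and the order holds there at Day 165. For example, at 50 kg with 10 mg held: 2,735/10,900 = 0.251 against 3,195/10,900 = 0.293. The 80–100 kg columns have an extra 14-day step, so CRmin falls on Day 161 and a later rollover is needed. At 80 kg with rollover on Day 179: 2,240 + 350 + 280 + 315 + 74×10 = 3,925 mg, over 80 × 218 = 17,440, gives 0.225. Remission to Day 211 gives 4,245/17,440 = 0.243.

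**Prednisone-related SAE, rollover on Day 63, not coded lack of efficacy.** 75 kg, one dose step every 3 weeks: 21 × (35 + 55 + 75) = 3,465 mg.
- Divisor 218, 0 mg after exit: 3,465/16,350 = **0.212**
- Per observed day: 3,465/(75 × 63) = **0.733**
- Record flagged ongoing and extended to Day 218: (3,465 + 155 × 75)/16,350 = **0.923**

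**Dose left out after a Day 63 exit.** Assume the true later dose lies between 10 mg/day and 1.0 mg/kg. The omission is 155 × (10/75)/218 = 0.095 to 155 × 1.0/218 = 0.711 per participant. Each 10 percentage points of such exits would move an arm mean by 0.009 to 0.071.

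**ICE exits.** A lack-of-efficacy ICE with the same doses to Day 63 scores 0.733 if the divisor also ends at the ICE, or 0.212 if it stays 218. Appendix 9.1 speaks of NCPD itself, which favours ending both. SAP 4.1.2.2 mentions only the cumulative dose.

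**The case against.** A fixed planned period is a legitimate choice. It avoids giving a short spell at high dose a large weight, and it counts doses recorded in follow-up. The SAP does not ignore missing doses: SAP 3.5.3 plans prednisone line plots under complete-case, last-observation and baseline-observation handling. SAP 6.1 reprints the formula with the period duration as divisor. All of this stands. But no NCPD test uses another rule for unrecorded days: the Mann-Whitney test and the treatment-policy analysis state none. SAP 6.1 contrasts only the weight with the protocol and names neither the 218 days nor the 0 mg rule.

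The example is also favourable in its timing. Protocol 4.2 expects CRmin at 24 to 30 weeks for most participants on active treatment. With CRmin on Day 168 and lesions lasting 7 days, at most 36 days at 10 mg are lost before Day 211, or 360/16,350 = 0.022. The order stays, but the gap is smaller than 0.028 (0.230 − 0.202).

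A reader might infer more than the documents support:
- **That 0 mg after exit is certain.** It is the literal result. A record flagged ongoing could be carried past exit, and the SAP does not say.
- **That treatment failures score below responders in the tested analysis.** That needs the 218-day divisor after a lack-of-efficacy ICE, and Appendix 9.1 favours the other reading.
- **That the Day 165 example fits every weight.** At 80–100 kg it falls four days after CRmin, too soon for new lesions that must fail to heal within a week.
- **That every W31 rollover is materially affected.** Days 212–218 at 10 mg/day are worth 70/16,350 = 0.004.

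**Conclusion.** The point holds and should be fixed. As written, the tested NCPD depends on how long a participant was observed in 1904 as well as on how much prednisone was taken. For exits outside its ICE list, a worse course can score lower than sustained remission: 0.202 against 0.230 at 75 kg, or 0.199 against 0.213 with taper. One Day 63 exit can score 0.212, 0.733 or 0.923, depending on the divisor and on how an ongoing record is handled.

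This rests on the literal no-record rule, on assumed dose paths and exit days, and on prednisone doses in 1905 not being linked. Early-exit rates by arm and reason are not given, so the size and direction of any effect on the treatment difference are unknown. A reader might infer inflated type I error or a bias in favour of efgartigimod. The documents show neither. For ICE exits the problem is narrower: one sentence should settle the divisor.

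**What to change.** In SAP 3.5.2, 4.1.2.2 and 9.1:

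1. Assign 0 mg only to days under observation in 1904 with no prednisone use.
2. State one divisor for ICE exits and one for non-ICE exits, and say whether records flagged ongoing stop at exit or are extended.
3. Add a sensitivity analysis of the tested NCPD per observed day, or with linked 1905 doses, reported beside the fixed-period result. Note that per-observed-day scoring gives short high-dose exposure a large weight.
4. In SAP 6.1, name the 218-day divisor and the 0 mg rule, or their replacement, as a change from the protocol's days in study and days treated.

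The cost is SAP wording and reprogramming of one derived variable before unblinding. Per-observed-day scoring needs no new data. Linking 1905 doses needs a cross-study merge.
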